## **3. STUDY OBJECTIVES**

### **3.1. Primary Objective**

The primary objective of this study is to assess the safety of nivolumab (Cohort 1) and combination of nivolumab/lirilumab (Cohort 2).

### 3.2. Secondary Objectives

The secondary objectives of this study are:

- To assess the change in CD8+ TIL density from pre-treatment Transurethral Resection of Bladder Tumor (TURBT) to post-treatment Radical Cystectomy (RC) tissues separately in patients treated with nivolumab or combination of nivolumab/lirilumab.
- To assess percentage (%) change in CD8+ TIL density from pre-treatment TURBT to post-treatment RC tissues separately in patients treated with nivolumab and combination of nivolumab/lirilumab.
- To describe the rate of patients in each cohort who do not get RC within 6 weeks after completion of neoadjuvant treatment specifically and directly related to treatment-related adverse events (AEs).
- To assess the antitumor efficacy of nivolumab and combination of nivolumab/lirilumab as measured by pathologic complete (pT0N0) and partial (<pT2N0) response rate in the two cohorts.
- To assess the rate of recurrence-free survival (RFS) at the two-year time point from the time of registration in patients treated with nivolumab and combination of nivolumab/lirilumab.
- To assess the prognostic and predictive value of the expression of baseline immunohistochemistry (IHC) markers of interest (e.g. PD-1, PD-L1, PD-L2, NKG2D, KIR2DL1/2/3), and change in expression, for pathologic partial and complete tumor response (defined by cystectomy pathologic staging <pT2N0 and pT0N0, respectively), in patients treated with nivolumab and combination of nivolumab/lirilumab.
- To assess the prognostic and predictive value of peripheral blood mononuclear cell (PBMC) T-cell subset status (%CD4+ T-cells, %CD8+ T-cells, %Treg T-cells, %Myeloid Derived Suppressor Cells, %Natural Killer cells, etc.) and change in status, as assessed by flow cytometry analysis, for pathologic partial and complete tumor response (defined by cystectomy pathologic staging < pT2N0 and pT0N0, respectively), in patients treated with nivolumab and combination of nivolumab/lirilumab.

### 3.3. Exploratory Objectives

- To compare CD8+ TIL density in post-treatment RC tissues in patients treated with nivolumab and combination of nivolumab/lirilumab.
- To assess the prognostic and predictive relationship between pre- and post- treatment TIL and NK-cell level and activation and pathologic partial and complete response (defined by cystectomy pathologic staging <pT2N0 and pT0N0, respectively) as well as two-year RFS, in patients treated with nivolumab and combination of nivolumab/lirilumab.
- To assess impact of prior BCG exposure on rates of pathologic partial and complete response (defined by cystectomy pathologic staging <pT2N0 and pT0N0, respectively) as well as two-year RFS, in patients treated with nivolumab and combination of nivolumab/lirilumab.
- To assess the prognostic and predictive relationship of tumor mutational load, neo-epitope burden, intrinsic molecular subtypes (basal vs. luminal), and T-cell clonality with pathologic partial and complete response (defined by cystectomy pathologic staging <pT2N0 and pT0N0, respectively) as well as two-year RFS, in patients treated with nivolumab and combination of nivolumab/lirilumab.
- To assess the prognostic and predictive relationship of pre- and post-treatment peripheral blood T-cell subsets, CD4+/CD8+ and CD4+/FOXP3+ ratios and plasma cytokine multiplex panels with pathologic partial and complete response (defined by cystectomy pathologic staging <pT2N0 and pT0N0, respectively) as well as two-year RFS, in patients treated with nivolumab and combination of nivolumab/lirilumab.
- To assess the prognostic and predictive relationship between pre- and post-neoadjuvant treatment levels in plasma cytokine biomarkers of interest (e.g. IFN- $\alpha$ , TGF- $\beta$ , IL-10, IL-4, IL-5, IL-13, IFN- $\gamma$ , etc.) and pathologic partial and complete response (defined by cystectomy pathologic staging <pT2N0 and pT0N0, respectively) as well as two-year RFS, in patients treated with nivolumab and combination of nivolumab/lirilumab.
- To assess prognostic and predictive associations between baseline tumor and/or tumor infiltrating lymphocyte tissue and ctDNA genomic alterations, gene expression, and methylation signatures for pathologic partial and complete response (defined by cystectomy pathologic staging <pT2N0 and pT0N0, respectively) as well as two-year RFS, in patients treated with nivolumab and combination of nivolumab/lirilumab.

- To assess prognostic and predictive value of serum circulating antibody profiles on pathologic partial and complete response (defined by cystectomy pathologic staging <pT2N0 and pT0N0, respectively) as well as two-year RFS, in patients treated with nivolumab and combination of nivolumab/lirilumab.
- To assess CD8+ TIL density by central pathology review using image analysis in both cohorts.

## 4. STUDY DESIGN

### 4.1. General Study Design and Plan

This is a Phase Ib open-label clinical trial for patients with cisplatin-ineligible MIBC (T2-T4a, N0-N1, M0). Patients will be sequentially enrolled first into Cohort 1 treated with nivolumab alone (N=12). In the absence of the occurrence of high rate of treatment related AEs as defined in protocol Section 5.4 and 13.1.1 with neoadjuvant nivolumab treatment, the study will proceed with enrollment into Cohort 2 of neoadjuvant treatment with combination nivolumab/lirilumab. (In both cohorts, neoadjuvant treatment must start within 8 weeks of transurethral resection of the first TURBT that showed muscularis propria invasion). Each group will receive a total of 4 weeks (week 0 and 4) of neoadjuvant therapy followed by radical cystectomy (RC) with bilateral (standard or extended) pelvic lymph node dissection (PLND).

The RC with bilateral (standard or extended) PLND will occur as soon as possible but within 6 weeks after the last neoadjuvant dose in either cohort.

Off treatment visit will occur approximately 30 days following cystectomy (cystectomy is not performed, Off Treatment visit should be performed at next scheduled appointment or treating physician discretion, as clinically indicated) and patients will be followed for 100 days after neoadjuvant treatment for AEs. Adverse events may be reviewed at the next visit  $\geq$  100 days after last dose of neoadjuvant therapy or phone follow-up may be done to review adverse events.

Patients will be followed clinically and radiographically for at least 2 years post-cystectomy or when study-wide follow-up ends per standard of care. Date of diagnosis for recurrence, first subsequent therapy and survival shall be reported. Phone follow-up may also be done for patients unable or unwilling to return for follow-up evaluations.

#### **4.2. Study Population**

The study will aim to screen 43 eligible patients in order to enroll 36 patients in the trial (assuming about 20% tumor tissue assessment screen failure rate). Estimate at least 2-3 patients per month at approximately 8 sites. The estimated time for accrual completion will be approximately 18 months.

#### **4.3. Treatment Administration**

Neoadjuvant treatment must start within 8 weeks of transurethral resection of the first bladder tumor (TURBT) that showed muscularis propria invasion.

##### **4.3.1. Study treatment**

Patients enrolled in the trial will be administered one of two of the following treatment regimens:

Cohort 1: Nivolumab 480 mg IV every 4 weeks for 2 neo-adjuvant doses (week 0 and 4).

Cohort 2: Nivolumab 480 mg IV + lirilumab 240 mg IV every 4 weeks for 2 neo-adjuvant doses (week 0 and 4).

##### **4.3.2. Dose Delays**

A +/-3 day window is allowed for scheduled therapy. Dose delays are permitted. NO dose modifications will be allowed.

### **4.3.3. Discontinue treatment**

If the Grade 3 toxicity does not resolve to  $\leq$  Grade 1 within 21 days, all study therapy will be permanently discontinued.

If the patient experiences Grade 4 treatment related hematologic toxicity in either study cohort, all study therapy must be permanently discontinued regardless of the time to resolution  $\leq$  Grade 1.

## **5. EFFICACY MEASUREMENTS**

Patients should be evaluated for pathologic tumor response at post-treatment radical cystectomy time point. Tumor recurrence will be evaluated in this study using the new international criteria proposed by the revised Response Evaluation Criteria in Solid Tumors (RECIST) guideline Version 1.1 (Protocol Appendix V).

Efficacy measurements listed below:

### **5.1. Tumor Response**

Only those patients who have received at least one dose of therapy, and undergo radical cystectomy will be considered evaluable for tumor response. RECIST response assessments will be performed locally for the trial.

### **5.2. CD8+ T-Cell Density**

The CD8+ T-cell density is defined as the number of CD8+ tumor-infiltrating T-cells per 100 tumor cells within a 400x high power field (HPF).

The CD8+ T-cell density will be calculated as:

Tumor Infiltrating CD8+ T-cell density (CD8+ T-cells per 100 tumor cells) = (Total # of CD8+ TILS)/ (Total # of tumor cells per HPF) x 100

Five representative tumor fields with the greatest gross tumor infiltrating lymphocyte fields (minimum 100 tumor cells per representative field) will be chosen for measurement by microscope analysis by the pathologist with the final CD8+ T-cell density determined as the mean of the CD8+ T-cell density across the five fields.

### **5.3. %CD8+ Tumor-Infiltrating T-Cells**

The %CD8+ tumor-infiltrating T-cells will be quantified by immunohistochemistry (IHC) analysis of tissue. Using semi-automated image analysis, a staining percentage determined by dividing the area of brown 3,3'-Diaminobenzidine (DAB) staining by the area of epithelial cells will be obtained.

Five representative tumor fields with the greatest gross tumor infiltrating lymphocyte fields will be chosen for measurement by the pathologist with the final %CD8+ tumor-infiltrating T-cells determined as the mean of the %CD8+ tumor-infiltrating T-cells across the five fields

### **5.4. Pathologic Tumor Response Definitions**

Pathologic response (<ypT2N0M0) is defined by post-treatment radical cystectomy tumor stages with N0 and M0 status with the following T-stages: T0, Ta, Tis, T1.

Pathologic tumor stage reported according to American Joint Commission on Cancer (AJCC) Staging system T, N, M categories for bladder cancer (SAP Appendix II).

#### **5.4.1 Pathologic Complete Response**

Pathologic response (ypCR) is defined by post-treatment radical cystectomy tumor stages with N0 and M0 status with the following T-stages: T0.

#### **5.4.2 Pathologic Non-Response**

Pathologic non-response (ypNR) is defined by post-treatment radical cystectomy tumor stages with any node-positive (N1, N2, N3) or metastases-positive (M1) status. In addition, patients with N0 and M0 status with the following T-stages are also classified as pathologic non-responders: T2, T2a, T2b, T3, T3a, T3b, T4, T4a, T4b.

### 5.5. Tumor IHC Staining Intensity Definitions

For validated IHC targets, standardized IHC staining intensity cutoffs will be utilized. For all other IHC targets, IHC staining will be categorized as:

Grade	Stain
0	<1% cells stained
1+	1 to <5% cells stained
2+	5 to 10% cells stained
3+	≥ 10% cells stained

### 5.6. Recurrence-Free Survival (RFS) as per RECIST 1.1

Recurrence is defined as the Progressive Disease (PD) in Overall Response assessed by ERECIST 1.1 or death after radical cystectomy. RFS time is defined as the duration of time from start of treatment to time of first documented recurrence (after radical cystectomy) or death, whichever occurs first.

### 5.7. Overall Survival (OS)

OS is defined as the duration of time from start of treatment to time of death.

### 5.8. Other Efficacy Measurements

ECOG performance status will be assessed at screening, TURBT, day 1 at each infusion, surgery and at the off treatment visits.

## 6. SAFETY MEASUREMENTS

Safety will be evaluated by

- Adverse events
- Concomitant medications and procedures
- Clinical laboratory tests,
- Physical examination findings,
- Vital signs measurements, and

### 6.1. Adverse Events

**Adverse Event (AE)** is defined as any new untoward medical occurrence or worsening of a pre-existing medical condition in a patient administered a medicinal product in a clinical investigation and which does not necessarily have a causal relationship with this treatment. An AE can therefore be any unfavorable and unintended sign (e.g., including an abnormal laboratory finding), symptom, or disease temporally associated with the use of a product (investigational or marketed), whether or not considered related to the product (investigational or marketed).

After informed consent, but prior to initiation of study treatment (nivolumab and lirilumab), only AEs/SAEs caused by a protocol-mandated intervention will be collected (e.g., SAEs related to invasive procedures such as biopsies). After the initiation of study treatment, all identified AEs and SAEs must be recorded and described on the appropriate page of the electronic Case Report Form (eCRF). If known, the diagnosis of the underlying illness or disorder should be recorded, rather than individual symptoms. The following information should be documented for all AEs: date of onset and resolution, severity of the event; the investigator's opinion of the relationship to investigational product (see definitions below); treatment required for the AE; cause of the event (if known); and information regarding resolution/outcome.

Only clinically significant laboratory abnormalities that require active management will be recorded as AEs or SAEs on the eCRF (e.g., abnormalities that require study drug dose delay, discontinuation of study treatment, more-frequent follow-up assessments, further diagnostic investigation, etc.).

The categories and definitions of severity used for clinical trials AEs are defined in the NCI's Common Terminology Criteria (CTCAE) V5.0 (<http://www.ctep.cancer.gov>).

The categories of causal relationship or attribution to study drug are presented as Definite, Probable, Possible, Unlikely, Unrelated. Categories 'Definite', 'Probable' and 'Possible' are considered study drug related. Categories 'Unlikely' and 'Unrelated' are considered not study drug-related.

AEs related to nivolumab and liriumab should be followed for 100 days after last dose of study therapy until  $\leq$  grade 1 or stabilization, and reported as SAEs if they become serious. Any AE's (serious or not) that occur more than 100 days after the last dose of study therapy but that are deemed to be at least possibly related to study therapy shall be reported.

## **6.2. Concomitant Medications and Procedures**

Concomitant medications and procedures will be collected during the trial and recorded in the CRF page.

## **6.3. Clinical Laboratory Assessments**

Clinical laboratory tests will be collected at screening, day 1 of cycles 1 through 4, end of cycle 4, day 1 of each additional cycle and day 1 of cycle 9 or end of treatment.

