7.2.1 Grade 1 and Grade 2 Toxicities

No dose interruptions will be performed for Grade 1 or 2 non-hematologic toxicities, except for:

- Any grade hypophysitis, meningitis, immune-related neurological AEs
- Any Grade 2 drug-related uveitis, eye pain, or blurred vision that does not respond to topical therapy and does not improve to Grade 1 severity within the retreatment period OR requires systemic treatment will require permanent discontinuation.
- Colitis (Grade 2)
- AST, ALT, bilirubin (Grade 2)
- Pneumonitis (Grade 2)
- Nephritis (Grade 2)

- Infusion reaction that does not resolve within an hour of stopping infusion (Section 7.3 for Infusion Reaction Guidelines), or
- Other intolerable or persistent Grade 2 drug-related AE, as per physician discretion.

Discontinue treatment for persistent Grade 2 immunologic AEs (such as colitis, pneumonitis, and nephritis) that do not recover to Grade 1 or resolve within 6 weeks after the last dose of study drug (Exceptions: rash, fatigue, amylase/lipase elevations, other electrolyte abnormalities).

In addition, discontinue treatment for persistent Grade 2 ALT, AST, or bilirubin that do not recover to Grade 1 or resolve within 6 weeks after the last dose of study drug. A thorough investigation of the cause of the ALT, AST, or total bilirubin elevation is recommended including the exclusion of other causes – e.g. concurrent medications, infection, injury, hypo-perfusion, and alcohol consumption. Close monitoring of hepatic labs at least weekly and consideration of imaging such as ultrasound of the liver is suggested.

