## **7.6. Safety Analysis**

The safety evaluations include AEs, concomitant medication, clinical laboratory assessments, vital signs, and physical examination. Safety analysis will be assessed for the safety population.

The results of this study will be reported using summary tables, figures, and data listings. Continuous variables will be summarized using mean, SD, median, minimum, and maximum. Categorical variables will be summarized by presenting the number (frequency) and percentage in each cohort.

If any screening safety data is repeated, the measurement taken closest to dosing will be used in the analysis as pre-study baseline. If any post-dose safety data is repeated, the measurement taken first at the particular visit in question will be used in the analysis.

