#### **7.6.7. Clinical Laboratory Data**

Numeric clinical laboratory data will be summarized at each visit (clinical data collection point) using descriptive statistics. Non-numeric laboratory tests will be summarized separately using frequency counts on unique responses. Individual change from baseline in lab values will be calculated and summarized descriptively. The Lab shift table will be displayed at each visit for each laboratory test.

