## **12. APPENDIX**

**12.1. Appendix I. Study procedure and Parameters**

1. All pre-study assessments and scans should be done  $\leq 4$  weeks prior to registration with exception of first TURBT that showed muscularis propria invasion which can be done within 56 days.

Procedures	Screening	TURBT  (if needed)	Infusion 1	Infusion 2*	Surgery	Off Treatment 	Follow-Up 
			Day 1	Day 1			
Written Informed Consent	X						
Pathology 	X 	X 					
Disease Characteristics 	X						
Medical/Surgical History	X						
Assessment of Baseline Signs & Symptoms	X						
Height	X						
Physical Exam including Weight	X	X	X	X	X	X	
Vital Signs  (Temperature, Pulse, Blood Pressure)	X	X	X	X	X	X	
Performance Status	X	X	X	X	X	X	
CBC/Differential/Platelets 	X	X	X	X	X	X	

Procedures	Screening	TURBT  (if needed)	Infusion 1	Infusion 2*	Surgery	Off Treatment 	Follow-Up 
			Day 1	Day 1			
Chemistry 	X	X	X	X	X	X	
Hepatitis B & C Testing 	X						
TSH, FT3, FT4 	X			X 	X	X	
Serum Pregnancy Test 	X		X 	X 			
Serum Cortisol Level	X				X		
ECG	X						
Chest/Abdomen/Pelvic CT with Contrast or MRI 	X				X 		X
Research Blood Specimens 	X ( Streck DNA tube only)		X	X	X	X	X 
Research Urine Specimens 			X	X	X	X	X 
Research Tissue Specimens 		X			X		X 
Treatment Administration 			X	X			
Oxygen Saturation by Pulse Oximetry 			X	X			

Procedures	Screening	TURBT  (if needed)	Infusion 1	Infusion 2*	Surgery	Off Treatment 	Follow-Up 
			Day 1	Day 1			
Radical Cystectomy with Pelvic Lymph Node Dissection 					X		
Concomitant Medication Review	X		X	X	X	X	
Adverse Events Assessment			X	X	X	X 	
Survival Status							X

\* **Scheduled Visits:** +/-3 day window is allowed for scheduled study therapy, required tests and/or visits except as otherwise noted. Delay due to holidays, weekends, bad weather or other unforeseen circumstances will be permitted.

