- 1 Cystoscopy with TURBT showing muscularis propria should be performed within 8 weeks (56 days) of starting study therapy. Patients must have sufficient baseline tumor tissue from either the initial or repeat TURBTs. **Tumor tissue content for CD8+ T-cell density assessment must be qualified as sufficient (≥ 20% tumor content in the specimen in initial or repeat TURBT with highest tumor content) for analysis and must be documented by the local pathologist prior to registration.** (The actual CD8+ T-analysis does not need to be done by the Central Laboratory prior to registration.) This documentation can occur at any time prior to registration. Patients will complete all other screening studies (i.e. labs, imaging, history, exam, etc.) within 28 days of starting study therapy.
- 2 Record date of diagnosis and stage.
- 3 Patients will have Temperature, Pulse and Blood Pressure taken at each visit. In addition, patients will have their blood pressure and pulse measured before, during and after the infusions at the following times:
  - At the beginning of the infusion
  - After nivolumab infusion and before lirilumab infusion for patients receiving lirilumab
  - At the end of the infusion
- 4 CBC with differential and platelet count which includes WBC, ANC, Platelets, Hemoglobin, and Hematocrit required prior to each dose of study therapy. Results known prior to treatment administration.

- 5 Albumin, BUN/creatinine, uric acid, sodium, potassium, chloride, glucose, calcium, alkaline phosphatase, AST, ALT, total bilirubin, and total protein.
- 6 Hepatitis B surface antigen (HBsAg), and Hepatitis C (HCV) testing within 4 weeks of registration. These tests may be repeated during the course of the study, if clinically indicated.
- 7 TSH, FT3, FT4 at Screening and before Infusion 2, Day 1.
- 8 Required for sexually active females of child-bearing potential. Infusion 1 and Infusion 2: Must be within 24 hours prior to treatment with nivolumab.
- 9 CT with IV contrast is the preferred method. MRI exams of the chest/abdomen/pelvis may be performed, if CT of chest/abdomen/pelvis cannot be obtained.
- 10 Research blood and urine samples shall be obtained at time points noted below. Refer to Section 14 for details. **NOTE: Blood draw order is specified in the PrE0807 Lab Manual.**

Screening

One 10 mL Streck DNA tube (for germline)

Before First and Second Neoadjuvant Dose

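### SAP 6.3 schedules laboratory tests by cycles that this two-infusion trial does not have, and the by-visit laboratory tables come with no worst-value summary and no rule for unscheduled results

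*SAP*

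**What the plan says.** SAP 6.3 sets out when laboratory data are collected: "Clinical laboratory tests will be collected at screening, day 1 of cycles 1 through 4, end of cycle 4", followed by "day 1 of each additional cycle and day 1 of cycle 9 or end of treatment". SAP 4.3.1 describes the treatment differently: "Cohort 1: Nivolumab 480 mg IV every 4 weeks for 2 neo-adjuvant doses (week 0 and 4", with the same two dosing times for Cohort 2.

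The visit grid in SAP Appendix I, like the grid in protocol Section 11, has columns for Screening, TURBT, two infusions, Surgery, Off Treatment and Follow-Up. Footnote 7 to the SAP grid reads "TSH, FT3, FT4 at Screening and before Infusion 2, Day 1".

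The analysis rules are elsewhere. SAP 7.6 states: "If any post-dose safety data is repeated, the measurement taken first at the particular visit in question will be used in the analysis". SAP 7.6.7 summarises numeric results and changes from baseline by visit and adds: "The Lab shift table will be displayed at each visit for each laboratory test". Neither section mentions results obtained outside a scheduled visit, or a worst post-baseline value. Protocol 7.2.1, on persistent Grade 2 ALT, AST or bilirubin, suggests "Close monitoring of hepatic labs at least weekly".

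**The concern.** There are two separate weaknesses.

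First, the collection schedule in SAP 6.3 does not describe this trial. A programmer or data manager working from 6.3 would look for visits that do not exist and would find no mention of Surgery. Surgery is the first scheduled laboratory point after the second dose and, in both grids, the only post-dose point for serum cortisol.

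Second, even with the schedule corrected, the laboratory tables as described hold one value per patient per scheduled visit. A higher value on a repeat at the same visit is not used, and a higher value between visits has no assigned place. In a trial of immune checkpoint therapy whose primary objective is safety, laboratory tables should show how far each patient's values moved at worst. They also serve as a check on adverse event recording that does not depend on an investigator's view of clinical significance.

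**Working it through.** No sample size, power or rate is in question, so the check compares the texts.

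**Step 1. Match SAP 6.3 to the grid.** SAP 6.3 names 7 fixed points: screening (1), day 1 of cycles 1 to 4 (4), end of cycle 4 (1), and cycle 9 or end of treatment (1). It also allows for any additional cycles. Assume that cycles 1 and 2 stand for the two infusions and that end of treatment stands for the Off Treatment visit.

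| Grid visit for "CBC/Differential/Platelets" and chemistry | Counterpart in SAP 6.3 |
|---|---|
| Screening | screening |
| TURBT (if needed) | none |
| Infusion 1 | cycle 1, by assumption |
| Infusion 2 | cycle 2, by assumption |
| Surgery | none |
| Off Treatment | end of treatment, by assumption |

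Four of the 6 grid visits match, and 6 − 4 = 2 are absent. In the other direction, 7 − 4 = 3 fixed points (cycle 3, cycle 4, end of cycle 4) have no counterpart, nor do any later cycles. The next section, SAP 6.4, lists infusions, surgery and end of treatment for physical examination, so the mismatch is confined to 6.3. SAP Section 8 declares no changes from the protocol's analyses, so 6.3 cannot be read as a deliberate departure.

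**Step 2. Thyroid tests.** The thyroid row in both grids marks Screening, Infusion 2, Surgery and Off Treatment. Footnote 7 in the SAP names only the first two. The protocol's footnote 7 gives no timing.

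**Step 3. What the analysis rules do with extra results.**
- A repeat at the same visit: SAP 7.6 keeps the first value. If the repeat is higher, the higher value is not used. If it is lower, the first value already shows the peak. The rule therefore hides some peaks, not all.
- A draw between visits: the rule in 7.6 is worded for repeats at a visit and does not cover it. SAP 7.6.7 works by visit. SAP 7.5.1 brings all safety data to the end of the study into the safety analysis, but no laboratory table is described that could show such a draw.

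**Step 4. Where extra results are foreseeable.** The infusions are 4 weeks apart, with no laboratory visit scheduled between them. Surgery may come up to 6 weeks after the second infusion, again with none between. If monitoring ran exactly weekly over a whole gap, up to 4 − 1 = 3 draws would fall in the first gap and up to 6 − 1 = 5 in the second. These are upper limits, because the suggestion applies only once a Grade 2 hepatic abnormality persists.

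The SAP's window for treatment-emergent events ends 100 days after the last dose. With surgery by 6 weeks (42 days) and the Off Treatment visit at 30 + 7 days, the last scheduled laboratory point is no later than 42 + 30 + 7 = 79 days after the last dose. Any laboratory result in the final 100 − 79 = 21 days or more is then unscheduled.

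**The case against.** The strongest reply is that little depends on these tables. SAP 6.3 describes collection; the rule for analysis is 7.6.7, which summarises every visit. A reader might infer from 6.3 that the tables would miss Surgery. The documents do not support that: blood counts, chemistry and thyroid tests are marked at Surgery in both grids, so the data are collected and fall within the planned summaries.

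A reader might also infer that the first-value rule discards unscheduled results. It does not say so. It covers repeats at a visit, and on unscheduled draws the SAP is silent.

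Nor is a serious peak lost to the trial. Protocol 9.1 and SAP 6.1 require clinically significant abnormalities needing active management to be recorded as adverse events, and they give closer follow-up and discontinuation of treatment as examples. A change in severity of the same abnormality is recordable. Protocol 7.2.2 makes drug-related Grade 3 or higher AST, ALT or bilirubin a reason for discontinuation, and protocol 9.4 makes potential drug-induced liver injury a serious adverse event. SAP 7.6.6.3 tabulates serious and Grade 3 or higher treatment-related events.

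Finally, the table shells are in a separate template that is not among the documents, and it may contain a listing of unscheduled results or a maximum-grade table.

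Most of this stands, and it limits the point to the laboratory tables. It does not remove it. The contradiction between 6.3 and the grids remains. Adverse event recording depends on judgement about clinical significance, so it is only a partial substitute for a systematic laboratory summary. A table that might exist in the template should still be specified in the SAP.

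**Conclusion.** The schedule in SAP 6.3 is wrong for this trial as written: it lists cycles that do not exist and omits 2 of the 6 visits at which blood counts and chemistry are taken, one of them Surgery. Footnote 7 conflicts with its own grid row. These are contradictions to reconcile, not evidence that data will be lost.

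The laboratory tables as described can understate peak abnormalities, because they use the first of repeated values, present shifts by visit, and give unscheduled results no place. The clearest case is hepatic, since that is where the protocol foresees extra draws. Nothing comparable in the cited text supports a specific claim about renal or endocrine understatement.

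The size of any understatement cannot be derived from the documents, and no figure in the plan changes. A reader might take one missed patient, 1/12 = 8.3 points in Cohort 1 or 1/24 = 4.2 points in Cohort 2, as the bias. Those figures are only the weight of one patient in each cohort; the SAP defines no laboratory toxicity rate to which they would apply. The primary endpoint (SAP 7.6.6.1) and the interim safety rules (SAP 7.8) are built on adverse events and are not affected.

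The conclusion assumes that the unseen table template adds no worst-value table. If it does, what remains is the text correction and a stated rule for unscheduled results.

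**What to change.** 1. In SAP 6.3, replace the cycle list with the Appendix I visits: Screening, TURBT if needed, Infusion 1, Infusion 2, Surgery and Off Treatment, with the tests at each as marked in the grid.
2. Reconcile footnote 7 of SAP Appendix I with the thyroid row it annotates.
3. In SAP 7.6.7, add a shift table from baseline to the worst post-baseline CTCAE v5.0 grade, for tests that can be graded, from first dose to 100 days after the last dose (the SAP's own treatment-emergent window). State that all recorded repeat and unscheduled results are used.
4. In SAP 7.6, restrict the first-value rule to by-visit summaries.

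The cost is SAP wording and one extra table. Isolated spurious values may become a patient's worst grade and would need a footnote. The table can use only unscheduled results that are entered in the eCRF as laboratory data. The documents do not say whether they are; if they are not, either extra data entry or a stated limitation is needed.
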